### **8.8. Analysis of the Exploratory and Additional Efficacy Endpoints**

The exploratory endpoints of the trial are:

- Time to the patient being prescribed and patient agrees to any of the following DME items (manual wheelchair, power wheelchair, augmentative and alternative and augmentative communication device, NIV and/or gastrostomy tube), time to first receipt, time to first use, time to daily use, time to dependence and number used of any of the specified DME items from baseline to the Week 24 and Week 48 as well as reasons to receive the above DME
- Changes from baseline to Week 24 and Week 48 in the four subdomain scores of the ALSFRS-R
- Time spent in each MiToS stage and number of patients to transition stages from baseline to Week 24 and Week 48
- Change from baseline to Week 48 in ALSFRS-R total score
- Change from baseline to Week 48 in FVC (liters)
- Change from baseline to Week 48 in grip strength
- Combined assessment of change in ALSFRS-R total score, time to dependence on assisted ventilation (either invasive or non-invasive), and survival time up to Week 48
- Changes from baseline to Week 24 and Week 48 in the mega-score of muscle strength measured by HHD in bilateral first dorsal interosseous muscles, abductor pollicis brevis muscles, and abductor digiti minimi muscles
- Changes from baseline to Week 24 and Week 48 in the EQ-5D-5L
- Changes from baseline to Week 24 and Week 48 in the EQ-Visual Analogue Scale (VAS)
- Time to event for first hospitalization to Week 24 and Week 48

Additional endpoints listed below will be analyzed:

- Time to event for all-cause death from baseline to Week 24 and Week 48
- Time to event for first hospitalization or all-cause death from baseline to Week 24 and Week 48

- Time to event for first ALS related hospitalization or all-cause death from baseline to Week 24 and Week 48
- Time to event for first ALS related hospitalization from baseline to Week 24 and Week 48
- Time to event for first ALS related hospitalization (without hospitalization for a PEG / RIG tube) from baseline to Week 24 and Week 48
- Time to event for first invasive mechanical ventilation by intubation or tracheostomy
- Time to event for first non- invasive mechanical ventilation
- Combined assessment of change in ALSFRS-R total score and survival time up to Week 24 and Week 48 (joint ranks analysis)
- Combined assessment of change in the percent predicted FVC, time to dependence on assisted ventilation (either invasive or non-invasive), and survival time up to Week 24
- Combined assessment of change in the ALSAQ-40 total score, time to dependence on assisted ventilation (either invasive or non-invasive), and survival time up to Week 24
- Change from baseline to Week 24 in FVC (liters)
- Change from baseline to Week 48 in percent predicted FVC
- Slope of change from baseline to Week 24 in percent predicted FVC
- Changes from baseline to Week 24 and Week 48 in forced expiratory volume in the first second
- Change from baseline to Week 24 and Week 48 in percent predicted FVC measured remotely
- Change from baseline to Week 48 in the ALSAQ-40 total score
- Changes from baseline to Week 24 and Week 48 in the subscores of ALSAQ-40
- Time to event for the first intrinsic hand muscle reaches zero from baseline to Week 24 and Week 48
- Time to event for all intrinsic hand muscles reach 0 from baseline to Week 24 and Week 48
- Progression in the degree use of both new and pre-existing DMEs from baseline up to Week 48

The following analyses will also be conducted if a systematic difference between in clinic measurements (from the Easy One spirometers) and remote measurements (from the NuvoAir spirometers) is not observed:

- Change from baseline to Week 24 and Week 48 in percent predicted FVC, with remote measurements collected in the same analysis windows as those used to substitute for the missing in clinic measurements.
- Change from baseline to Week 24 and Week 48 in percent predicted FVC measured in clinic and remotely. In clinic measurements take precedence if both in clinic and remote measurements are collected in the same analysis window.

### **8.8.1. Analysis of the Exploratory and Additional Efficacy Endpoint**

Exploratory analyses will be conducted based on the FAS and by the randomized treatment groups.

Proportional hazard Cox regression models will be applied for the time-to-event endpoints. For patients who had the events, the date of the first event will be used as the event date. For patients who did not have the event, data will be censored at the specified analysis time point (Week 24 or Week 48). Kaplan-Meier method will be used to summarize the time to event, and median, 95% CIs of the median, 1st and 3rd quartiles, and range will be provided.

The joint-rank test as described in [Section 8.7.1](#) will be used to analyze the endpoints of combined assessments up to the specified analysis time points, where the assessments of the endpoints will be used for ranking.

The MMRM as specified for the primary efficacy analysis (see in [Section 8.6.1](#)) except for the outcome variable, will be used for the endpoints of change from baseline to a specified time point.

A mixed linear model will be used for the endpoint of slope of change from baseline to a specified time point. The response variable will be the change from baseline to each post baseline visit up to the specified analysis time point, and the model terms will include treatment group, baseline value of the response variable, time from the first dose (a continuous variable), riluzole and edaravone use at baseline, treatment-by-baseline interaction and treatment-by-time interaction. The intercept will be set to zero.

In addition, descriptive statistics will be presented for time spent in each MiToS stage, transition of stages and progression in the degree use of both new and pre-existing DMEs (eg, from daily use progresses to dependence).

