4.2. Scientific Rationale for Study Design

CY 5031 is a Phase 3 clinical trial intended to evaluate the safety and efficacy of reldesemtiv for the treatment of patients with ALS, based on the results of a Phase 2 clinical trial, CY 5022. In

CY 5022, 458 patients with ALS were randomized 1:1:1:1 to 12 weeks of treatment with placebo versus reldesemtiv at 150 mg, 300 mg, or 450 mg twice daily. The primary efficacy analysis of the weighted dose response of change from baseline to 12 weeks in slow vital capacity (SVC, analyzed using a Mixed Model for Repeated Measures (MMRM) with multiple contrasts) was not statistically significant ($p = 0.11$); however, the decline in SVC was less than on placebo in all three reldesemtiv treatment groups (Figure 2).

Figure 2: CY 5022 Primary Endpoint – SVC Change from Baseline to Week 12

In a post-hoc analysis, the change from baseline to 12 weeks in the ALSFRS-R total score for all three reldesemtiv dose groups pooled versus placebo did achieve nominal statistical significance (LS mean difference = 0.9 points favoring reldesemtiv, $p = 0.01$; Figure 3). In addition, when the CY 5022 population was divided into tertiles based on the calculated rates of pre-study ALS progression, the apparent benefit of reldesemtiv in the three active treatment groups pooled versus placebo was particularly evident among the two faster progressing tertiles relative to the slowest progressing tertile (Figure 4). This replicates earlier observations that a reduction in measures of ALS disease progression by an intervention is less easily demonstrated among patients whose ALS was progressing relatively slowly prior to enrollment.

Figure 3: CY 5022 – ALSFRS-R Change from Baseline Over Time (All Active vs Placebo)

[figure not shown]
[figure not shown]

Figure 4: CY 5022 – Subgroup Analyses of ALSFRS-R Total Scores

*Pre-study rate of disease progression: 48 minus baseline ALSFRS-R total score divided by symptom duration in months

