**Methodology:**

This is a Phase 3, double-blind, randomized, placebo-controlled trial of reldesemtiv in patients aged 18 to 80 with ALS. The screening and qualification period for the trial will be no more than 21 days in duration. Approximately 555 eligible ALS patients will be randomized (2:1) to receive the following dose of reldesemtiv or placebo (stratified by riluzole use and edaravone use at baseline) for the first 24 weeks (double-blind placebo-controlled period):

- 300 mg reldesemtiv twice a day for a 600 mg total daily dose (TDD)
- Placebo twice daily

At the end of the 24-week double-blind, placebo-controlled period, patients will transition to the active drug period, where all patients will receive the following dose of reldesemtiv for the next 24 weeks:

- 300 mg reldesemtiv twice a day for a 600 mg TDD for patients who were not down titrated during the 24 weeks of blinded dosing
- 150 mg reldesemtiv twice a day for a 300 mg TDD for patients who were down titrated for any reason during the 24 weeks of blinded dosing

For the entire 48 weeks of dosing, patients and sites shall remain blinded to the randomized treatment assignment patients received during the first 24 weeks.

Study drug should be taken twice daily, morning and afternoon (at least 8 hours apart) and should be taken either with or within the 2-hour period following food.

For patients who complete Week 48 and want to enter the open label extension (OLE), they will not have the follow-up visit; instead, they will enter the OLE on the same day as their Week 48 visit. If the patient does not want to enter the OLE, or if the OLE has not yet been approved at the site, the follow-up visit will take place.

**Number of Subjects (planned and analyzed):** Approximately 740 patients will be screened in order to randomize/enroll approximately 555 patients, such that approximately 444 evaluable patients complete the 24-week of double-blind placebo-controlled period of the trial.

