### 4.3. Sample Size Considerations

#### 4.3.1. Sample Size Justifications

With a 2:1 randomization ratio to reldesemtiv and placebo groups, respectively, an initial sample size of approximately 555 patients is required to achieve at least 90% power to detect a 1.8 point treatment difference between reldesemtiv and placebo in the change from baseline to Week 24 in ALSFRS-R total score. This calculation is based on a two-sample t-test with two-sided alpha at 0.05 level, a common standard deviation of 5.5 points, and accounting for data missing and early treatment termination.

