### 4.4. Randomization

Eligible ALS patients will be randomized in a 2:1 ratio to receive 300 mg reldesemtiv twice daily or placebo twice daily, respectively, for the first 24 weeks (double-blind, placebo-controlled period). The stratification factors for randomization are baseline riluzole use and baseline edaravone use.

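### The exploratory Cox models in SAP 8.8.1 name no strata or covariates; fitted as written they are valid but give up power that baseline data already collected could recover

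*SAP*

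**What the plan says.** SAP 8.8.1 covers the exploratory and additional endpoints. For the time-to-event ones it states: "Proportional hazard Cox regression models will be applied for the time-to-event endpoints". It adds a rule for the event date, a rule for censoring at Week 24 or Week 48, and Kaplan-Meier summaries. It gives no strata and no covariates.

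No other section fills the gap. SAP 6.1 asks for a hazard ratio with interval and p-value but names no model terms. Protocol 9.4.1 and 9.4.4 name none either. The sample programs in SAP 12.5 contain no Cox code.

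On the design side, SAP 4.4 says: "The stratification factors for randomization are baseline riluzole use and baseline edaravone use". The trial also holds baseline values that may predict outcome. Protocol 4.2 defines one of them: "Pre-study rate of disease progression: 48 minus baseline ALSFRS-R total score divided by symptom duration in months". SAP 8.6.1 lists that rate, age and percent predicted FVC as candidates for the primary model, to be selected on blinded data.

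**The concern.** The omission stands out within 8.8.1 itself. The change endpoints are referred to the primary MMRM, the combined endpoints to the stratified joint-rank test, and the slope model is given term by term, including both randomisation factors. Only the Cox model has neither terms nor a cross-reference. The obvious way to program that sentence is with treatment alone.

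The hazard ratio is non-collapsible. If a covariate predicts the event and the treatment effect is not null, the ratio from a treatment-only model lies nearer 1 than the ratio conditional on the covariate, and the test has less power. At stake are the separate hazard ratios for death, hospitalisation, ventilation, device milestones and loss of hand-muscle strength, most of them at two time points. With the terms unstated, the adjustment set is also left to be chosen later across many models.

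**Working it through.** **1. The plan's own sample size.** The inputs in SAP 4.3.1 are: "This calculation is based on a two-sample t-test with two-sided alpha at 0.05 level, a common standard deviation of 5.5 points", "required to achieve at least 90% power to detect a 1.8 point treatment difference" and "With a 2:1 randomization ratio to reldesemtiv and placebo groups".

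- Placebo n = (1 + 1/2) × (1.960 + 1.282)² × 5.5² / 1.8² = 147.2, rounded up to 148.
- Total = 3 × 148 = 444, which matches the SAP's technical summary: "such that approximately 444 evaluable patients complete the 24-week of double-blind placebo-controlled period".
- 444/0.80 = 555, which matches "an initial sample size of approximately 555 patients". The 20% loss is implied by 444/555.

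Power at 444 is 0.902 (normal) or 0.900 (noncentral t). The figure reproduces and this point does not touch it. It concerns the primary endpoint only; the documents give no event rate, target hazard ratio or power for any Cox endpoint.

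**2. Which specified models account for riluzole and edaravone use.**

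| Model | SAP section | Factors included |
|---|---|---|
| Primary MMRM, reused for exploratory change endpoints | 8.6.1, 8.8.1 | yes |
| ANCOVA sensitivity analyses | 8.6.2, Table 5 | yes |
| Joint-rank test | 8.7.1 | yes (stratified) |
| MMRM for remaining secondary endpoints | 8.7.3 | yes |
| Slope model | 8.8.1 | yes |
| Cox models | 8.8.1 | not stated |
| Delayed-start comparisons | 8.8.2 | no model stated |

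**3. Size, by simulation under assumptions.** Set-up: 555 patients (370:185), exponential times, administrative censoring only, conditional hazard ratio 0.70. Riluzole use has prevalence 80% and edaravone use 25%, each with hazard ratio 0.8. One normal covariate has the SD shown on the log-hazard scale. There were 600 runs per row, so the simulation error on power is about √(0.5 × 0.5/600) = 2 points. All of these values except the 2:1 allocation and 555 are assumptions. Each cell gives hazard ratio, power.

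| Placebo event rate | Covariate SD | Treatment only | Stratified only | Both factors + covariate |
|---|---|---|---|---|
| 10% | 0 | 0.704, 21.3% | 0.702, 21.8% | 0.701, 21.7% |
| 10% | 0.5 | 0.702, 22.7% | 0.702, 22.0% | 0.698, 23.2% |
| 10% | 1.0 | 0.736, 15.5% | 0.736, 17.0% | 0.716, 20.0% |
| 30% | 0 | 0.702, 52.0% | 0.701, 51.8% | 0.701, 51.3% |
| 30% | 0.5 | 0.718, 48.0% | 0.717, 48.7% | 0.707, 52.2% |
| 30% | 1.0 | 0.741, 42.2% | 0.740, 41.5% | 0.699, 52.2% |
| 60% | 0 | 0.698, 84.7% | 0.696, 85.3% | 0.695, 85.7% |
| 60% | 0.5 | 0.724, 75.5% | 0.722, 75.2% | 0.697, 84.3% |
| 60% | 1.0 | 0.761, 61.7% | 0.760, 61.5% | 0.695, 85.3% |

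- Full adjustment against treatment only: at 30%, +4.2 points (SD 0.5) and +10.0 (SD 1.0). At 60%, +8.8 and +23.6. At 10%, +0.5 and +4.5. With a covariate of no prognostic value, nothing beyond noise.
- Stratification alone: the hazard ratio moves by at most 0.002 and power by no more than noise.
- With a true hazard ratio of 1, the three models give mean ratios of 0.997 to 1.011 and rejection rates of 3.8% to 6.7%. That is 5% within simulation error.

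**4. Where the gain comes from.** A standard approximation for the standard error of the log hazard ratio is √(1/[(2/3)(1/3)D]), with D the number of events. It contains no covariate term.

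- 30%, SD 1.0, D = 142: SE = 0.178. Treatment only: z = 0.2998/0.178 = 1.68, power Φ(1.68 − 1.96) = 39%. Adjusted: z = 0.3581/0.178 = 2.01, power 52%.
- 60%, SD 1.0, D = 298: SE = 0.123. Treatment only: z = 0.2731/0.123 = 2.22, power 60%. Adjusted: z = 0.3638/0.123 = 2.96, power 84%.

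These agree with the simulated powers to about 3 points, using the same standard error for both models. A separate simulation (hazard ratio 0.65, covariate hazard ratio 1.8 per SD) gave mean standard errors of 0.1731 unadjusted and 0.1738 adjusted at 25% events, and 0.1297 and 0.1305 at 45%. Adjustment does not shrink the standard error.

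**The case against.** The strongest reply is that the treatment-only model is not wrong. Its hazard ratio is a legitimate marginal quantity, its test is valid under the null, and neither document says that a conditional ratio is the target. That stands. A reader might infer that the unadjusted estimates are biased or less precise; they are neither. The case for adjusting is power.

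Second, the SAP is silent; it does not prescribe an unadjusted model. Its reference to analysis by randomised group applies to all exploratory analyses, including the adjusted MMRM, and 12.5 leaves final code to be settled before lock. This also stands: a treatment-only fit is the natural reading, not a stated one.

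Third, stratified randomisation is tempting as the main argument, but under the assumed effects those two factors recover almost nothing. They belong in the model for consistency with the design. The gain needs a prognostic covariate, and a reader might take pre-study progression rate to be the strongest one available. The documents list it only as a candidate and report no hazard associated with it. Several of the other models (joint-rank, ANCOVA, slope, remaining secondary MMRM) do not include it either, so adding it goes beyond matching them.

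Fourth, the largest gains need many events under a constant hazard ratio. If such rates are reached only by Week 48, placebo patients will have switched to reldesemtiv at Week 24, which makes a constant ratio doubtful. That limits the top of the range.

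**Conclusion.** The point holds as a minor, low-cost improvement. SAP 8.8.1 leaves the Cox models without strata or covariates, out of step with the other efficacy models that the SAP specifies. It cannot be said that every other model adjusts, because 8.8.2 states none.

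With a prognostic baseline covariate, a treatment-only fit costs about 4 to 10 power points at a 30% placebo event rate and just under 24 at 60% with covariate SD 1.0. The cost is nil if the covariate does not predict the event. When events are few it is small: at most about 4.5 points at 10%, where power is only 15% to 23% in any case. A separate run at about 5% events, roughly the level assumed for deaths, found an information gain (squared mean z) below 5%. Event rates, hazard ratios and covariate strengths are all assumed, so these figures show a range and are not a forecast.

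A reader might infer a threat to the trial's main result. There is none: the closed testing procedure in SAP 8.5 ends at Step 5 (handgrip strength), and the Cox endpoints lie outside it. Survival also enters the stratified joint-rank test, and Kaplan-Meier summaries and death counts are planned separately.

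**What to change.** Before database lock, add a statement to SAP 8.8.1 along these lines:

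- Cox models are stratified by, or include, baseline riluzole use and baseline edaravone use.
- They adjust for baseline ALSFRS-R total score and pre-study progression rate, or for the covariates selected on blinded data under 8.6.1.
- Where events are few, a reduced set of terms is used, under a rule fixed in advance on blinded event counts.
- The unadjusted hazard ratio is reported alongside as supportive, and the text says which ratio is marginal and which conditional.

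The cost is a few lines of SAP text and matching code; no new data are needed. The one drawback is sparse strata when events are few. The reduced set of terms deals with that, and little power is at stake in those analyses.

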7.2.1. Management of Patients after Permanent Discontinuation of Study Drug

If study drug is permanently discontinued, the patient should be encouraged to remain in the trial to continue to obtain outcome measures and safety data.

There are several options for a patient after permanently discontinuing study drug:

- Patient agrees to continue to return to clinic for all remaining in-clinic study visits and agrees to all planned remote visits.
- Patient only agrees to complete the early discontinuation (ED) visit as soon as possible after the decision is made, the follow-up visit 4 weeks after the last dose taken, and additional follow-up visits dependent upon lab results; it is preferred these are done in clinic but can be done remotely if that is not feasible.

- Patient only agrees to complete the ED visit; it is preferred this is done in clinic but can be done remotely if that is not feasible.
- Patient only agrees to remote visits to obtain patient study data. Patients should be strongly encouraged to come into the clinic for Week 24.
- Patient agrees to a mix of remote and in-clinic visits to obtain study data. Patients should be strongly encouraged to come into the clinic for Week 24.
- Patient only agrees to allowing contact for determination of vital status at Week 24 and Week 48
- Patient withdraws consent (see [Section 7.6](#)) and does not agree to any further study procedures or visits.

Assessments obtained at the early discontinuation and subsequent follow-up visit are listed in the Schedule of Activities. Details of the assessments to be performed at the additional visits following drug discontinuation, should the patient agree to be followed via either in-clinic or remote visits, can be found in the Study Manual.

Patients that have not withdrawn consent and have difficulty returning for all remaining study visits can be contacted by phone or video call to obtain patient study data.

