7.6. Patient Consent Withdrawal

Patients have the right to withdraw consent and no longer participate in the trial at any time and for any reason without prejudice to their future medical care by the physician or at the institution. Consent withdrawal means the patient no longer wishes to undergo any follow-up visits, study procedures, investigator contact, and non-patient contact follow-up (eg, medical records check).

- Discontinuing study drug should be distinguished from consent withdrawal for follow-up since the patient may agree to undergo study procedures or still be contacted even though they have stopped taking study drug.
- Consent withdrawal should be accompanied by documentation of the reason for withdrawal for patients willing to provide it. If the patient is unwilling to provide the reason, that should be recorded.

Patients who withdraw consent should be asked explicitly about the contribution of possible AEs to their decision to withdraw consent, and any AE information elicited should be documented.

Preferably, the patient should withdraw consent in writing and, if the patient or the patient's representative refuses or is physically unable, the site should document and sign the reason for the patient's failure to withdraw consent in writing; if the patient is unwilling to provide the reason, that too should be documented. The ICF for the trial should note that although a patient is free to leave the trial and stop taking study drug, the investigators hope the patient will remain for follow-up status evaluations.

For patients who have withdrawn consent for further follow-up, investigators and/or a third party retained by Cytokinetics may review public records as permitted by the ICF and applicable law to determine vital status of the patient at the end of the trial or before.

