7.7. Lost to Follow Up

A patient will be considered lost to follow-up if he or she repeatedly fails to return for scheduled visits and is unable to be contacted by the study site.

The following actions must be taken if a patient fails to return to the clinic for a required study visit:

- The site must attempt to contact the patient or the patient's family and reschedule the missed visit as soon as possible and counsel the patient on the importance of maintaining the assigned visit schedule and ascertain whether the patient wishes to and/or should continue in the trial.
- Before a patient is deemed lost to follow up, the investigator or designee must make every effort to regain contact with the patient or the patient's family (where possible, 3 telephone calls and, if necessary, a certified letter to the patient's last known mailing address or local equivalent methods). These contact attempts should be documented in the patient's medical record.

- Should the patient continue to be unreachable, he/she will be considered to have discontinued from the trial and are lost to follow-up.

Closing of specific sites or discontinuation of the trial are handled as part of Appendix 1 (Section 10.1.8).

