8.1.4. Muscle Strength

Muscle strength measurements of selected muscles will be performed using HHD at all in-clinic study visits as described in the Study Manual. If an in-clinic visit needs to become a remote visit, it will not be performed.

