#### **8.7.1.1. Imputation of the Missing Data for the First Secondary Efficacy Analysis**

Missing ALSFRS-R total score will be imputed for the first secondary analysis. See [Section 8.6.1.1](#) for the imputation method.

Every effort will be made to collect or derive vital status at Week 24 and Week 48. In the event that missing rate of vital status is higher than expected, the missing vital status will be imputed and sensitivity analyses will be performed.

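### SAP 8.8.1 censors every event-free patient at Week 24 or 48, so time after loss of follow-up counts as event-free in the exploratory non-fatal time-to-event analyses

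*SAP*

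**What the plan says.** SAP 8.8.1 applies Cox regression and Kaplan-Meier summaries to the FAS for all exploratory and additional time-to-event endpoints, with one censoring rule: "For patients who did not have the event, data will be censored at the specified analysis time point (Week 24 or Week 48". The endpoints, listed in SAP 8.8, include durable medical equipment milestones, ventilation, "Time to event for first hospitalization to Week 24 and Week 48", hospitalization-or-death composites, all-cause death, and "Time to event for the first intrinsic hand muscle reaches zero from baseline to Week 24 and Week 48".

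No other section supplies an exception. SAP 6.1 and protocol 9.4.1 only ask for counts of events and censored patients. Protocol 9.4.4 names time-to-event analyses without a censoring rule. SAP 6.8.1 deals with missing ALSFRS-R scores.

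The protocol foresees several kinds of incomplete follow-up:

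- After stopping drug (7.2.1), a patient may agree only to the early discontinuation visit, or choose this option: "Patient only agrees to allowing contact for determination of vital status at Week 24 and Week 48".
- On withdrawal (7.6): "Consent withdrawal means the patient no longer wishes to undergo any follow-up visits, study procedures, investigator contact".
- On loss of contact (7.7): "Should the patient continue to be unreachable, he/she will be considered to have discontinued from the trial and are lost to follow-up".
- On hand-held dynamometry (8.1.4): "If an in-clinic visit needs to become a remote visit, it will not be performed".

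The FAS (SAP 6.5.4) also admits dosed patients on recorded survival status alone, without a post-baseline efficacy assessment. For vital status, SAP 8.7.1.1 says: "Every effort will be made to collect or derive vital status at Week 24 and Week 48". No equivalent effort is described there for non-fatal events.

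**The concern.** Censoring should mark the last moment at which a patient was known to be event-free. A fixed date does that only for patients whose status is known to that date. For the others it amounts to imputing no event over all unobserved time. If nobody is censored before the analysis time point, one minus Kaplan-Meier is simply the proportion of the FAS with a recorded event.

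The endpoints are not equally exposed:

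- **Equipment, ventilation and hospitalization:** affected for any patient withdrawn, lost or followed for vital status only.
- **Hospitalization-or-death composites:** affected through the non-fatal part. A patient known only to be alive still has unknown hospitalization status.
- **Hand-muscle endpoints:** also affected in patients who stay in the trial but have no dynamometry at the endpoint visit because it was held remotely.
- **All-cause death:** the fixed date is correct when vital status is known at that date, and wrong only when it is not.

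At stake are the event curves and quartiles and, if loss differs between arms, the hazard ratios. Unequal loss is plausible. In the Phase 2 trial, ALT or AST above 3 times the upper limit occurred in 7.0% of patients on reldesemtiv and 0.9% on placebo (protocol 2.3.1), and hepatic criteria here require permanent discontinuation (protocol 7.4). Stopping drug is not itself loss of follow-up, so this shows plausibility and not size.

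**Working it through.** **Planning figure.** The plan states no figure for this rule. The nearest is the expected non-completion. With a difference of 1.8, SD 5.5, two-sided alpha 0.05, 90% power and 2:1 allocation, placebo n = 1.5 × (1.960 + 1.282)² × 5.5² / 1.8² = 147.2, rounded up to 148. The total is 3 × 148 = 444, and 444 / 0.80 = 555, as stated. The plan therefore allows for about 20% not evaluable or not completing. That includes early treatment termination, so it is not an estimate of lost event status.

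**Assumptions.** 24-week risk 30%, exponential event times, loss spread evenly over 24 weeks and independent of the event, 2:1 allocation, true hazard ratio 1.00. Loss by arm is not in the documents.

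**Event probability.** Let p = 0.30, Λ = −ln(0.70) = 0.3567, and d = the proportion lost. A lost patient has a recorded event with probability 1 − p/Λ = 1 − 0.30/0.3567 = 0.159. The rule then estimates (1 − d) × 0.30 + d × 0.159:

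- d = 5%: 0.285 + 0.0079 = 29.3%
- d = 10%: 0.270 + 0.0159 = 28.6%
- d = 20%: 0.240 + 0.0318 = 27.2%

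Simulation gives the same three values. Censoring at last contact gives 30.0% each time.

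**Hazard ratio.** Cox fits used 1,500,000 patients per scenario (Monte Carlo SE of the log hazard ratio about 0.003). For scale, 555 patients at 30% risk give 111 and 55.5 events, so SE(log HR) in the actual trial is about √(1/111 + 1/55.5) = 0.164.

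| Loss, reldesemtiv/placebo | HR, SAP rule | HR, last contact | Shift: abs. ln(HR) / 0.164 |
|---|---|---|---|
| 20% / 20% | 1.002 | 1.002 | 0.01 |
| 12% / 8% | 0.983 | 1.005 | 0.10 |
| 10% / 5% | 0.974 | 1.001 | 0.16 |
| 22.5% / 15% | 0.959 | 1.001 | 0.26 |
| 24% / 12% | 0.931 | 0.996 | 0.44 |
| 25% / 10% | 0.919 | 1.001 | 0.52 |
| 5% / 10% | 1.024 | 0.997 | 0.14 |
| 15% / 30% | 1.091 | 1.001 | 0.53 |

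Solving the large-sample Cox score equation numerically for the SAP rule agrees with every row to within 0.005. At 15% and 50% risk those limits differ from the 30% values by less than 0.003.

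**Type I error.** A second simulation used exponential dropout and 4,000 trials of 370 versus 185 patients, at 20% and 40% event risk. Rejection rates under the SAP rule were 4.9–5.4% at 20%/20% loss, 5.1–5.8% at 22%/16%, 7.0–8.2% at 24%/12% and 9.6–14.4% at 30%/10%. With last-contact censoring they were 4.7–5.3%.

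**Deaths.** With 30% latent event risk, 10% latent death risk and no other loss, the cumulative incidence is 0.3567/(0.3567 + 0.1054) × (1 − 0.70 × 0.90) = 0.772 × 0.37 = 0.286. Simulation under the SAP rule gives 0.285. Keeping patients who die at risk to the fixed date therefore yields a cumulative-incidence (subdistribution) quantity. That is legitimate, but the SAP does not say it is intended.

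**The case against.** The strongest reply is that the sentence is shorthand for administrative censoring of patients followed to the time point, that the SAP is merely silent on the rest, and that the final code would do the usual thing. The wording does not support this: it covers all patients without the event and offers no earlier date. SAP 6.4 also requires differences in analysis methods or data handling to be documented, so a programmer who departs from the rule needs a documented change.

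Other points against the concern do stand, and they limit it:

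- Moderate imbalances shift the hazard ratio by only 0.1 to 0.3 of its standard error. Type I error reached 7% or more only where one arm lost at least twice as many patients as the other.
- True loss of event status should be below the planned 20%. Patients who stop drug are encouraged to stay, phone or video contact is allowed, and equipment use is asked at every visit.
- Last-contact censoring recovers the truth here because loss was simulated as independent of the event. If loss tracks progression, that method is biased too.
- At 30% risk the 24-week median is not reached under either rule, so only the first quartile could move. No Week 48 sizes were computed.
- A remote Week 4 or Week 12 visit does no harm to the hand-muscle endpoints at the fixed date if dynamometry is done in clinic at Week 24.

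**Conclusion.** The concern holds. Followed as written, SAP 8.8.1 gives event curves for non-fatal endpoints that are too low whenever status is lost before Week 24 or 48. It also gives hazard ratios that lean toward the arm with more loss. Under equal loss of 5% to 20%, a 30% risk is understated by 0.7 to 2.8 percentage points and the hazard ratio is unaffected. Under the unequal loss examined in the table, a null hazard ratio moves to between 0.92 and 1.09. These sizes rest on assumed loss rates and on loss independent of the event.

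All affected analyses are exploratory or additional and lie outside the five-step hierarchy in SAP 8.5. The rule should be corrected before database lock, but it does not threaten the trial's main conclusions. The handling of death before a non-fatal event is only a matter of naming the estimand.

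**What to change.** Replace the sentence in SAP 8.8.1 with a rule that censors event-free patients at the earlier of the analysis time point and the last date they were known to be free of that event:

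- **Equipment, ventilation and hospitalization endpoints, including the composites:** the last contact or assessment at which that status was ascertained. A contact for vital status only does not extend this date.
- **Hand-muscle endpoints:** the last dynamometry date.
- **All-cause death:** the last date with known vital status.

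For non-fatal endpoints, add how death is handled. One option is to censor at death for a cause-specific hazard ratio and report cumulative incidence with death as a competing event.

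The cost is a few sentences and a small set of endpoint-specific derived dates. No new data collection is needed. The last contact date is already listed under SAP 7.1, but it cannot be used unmodified for patients whose last contact was for vital status only.
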